challenges. Moreover, based on its administration by a healthcare professional (HCP) every two months, the implementation for CAB-LA in real-world settings affords HCPs new opportunities to engage with patients, especially those with high unmet needs, which may influence PrEP persistence, retention-in-care, and patient-reported outcomes (PROs). To support adoption of CAB-LA for HIV PrEP, real-world studies are urgently needed to evaluate the impact of CAB-LA on outcomes that are critical to successful HIV prevention, such as adherence, persistence, retention-in-care, and PROs. Additionally, given its mode of administration, studies are needed to elucidate barriers to as well as facilitators for the implementation of CAB-LA PrEP in clinical settings. For people living with HIV, findings from the CUSTOMIZE study shed light on patient and provider perspectives on implementation of CAB+RPV LA for treatment of HIV. These insights from diverse settings of HIV treatment can serve as a springboard for evidence generation on the real-world use of CAB-LA for PrEP. Recognizing the need to support clinics in implementing and streamlining the delivery of PrEP, PRIME recently partnered with West Virginia Health Right (WVHR) in an implementation science initiative. Through this initiative, significant advances were made in overcoming barriers related to PrEP access. Specifically, the initiative directly resulted in a landmark decision by the Director of the West Virginia Medicaid program to remove all prior authorization requirements for CAB-LA for PrEP after attending the PRIME program. Building on this momentum and reduced barriers to CAB-LA access in WV, we propose to evaluate the implementation of CAB-LA supported by a novel PrEP mobile health app among underserved populations receiving care at WVHR. WVHR is a 501(c)3 non-profit, patient-centered, medical home that provides comprehensive primary and specialty care to >40,000 uninsured, underinsured, and underserved adults. Among services provided, WVHR provides HIV prevention care, harm reduction services, behavioral health care, and transgender health care—which is the only transgender health program in the region. Its in-house pharmacy fills >90,000 prescriptions annually,

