3.3.4. Evaluate the acceptability, barriers to, and facilitators for implementation of CAB-LA

4. STUDY DESIGN

4.1. Study Design

4.1.1. The research project follows a hybrid effectiveness-implementation research design, with the primary aim focused on evaluation of PrEP adherence, persistence and retention-in-care with CAB-LA compared with oral PrEP, and secondary aims focused on evaluating patient-reported outcomes (PROs), implementation of a digital health intervention to support adherence and persistence, and evaluating contextual factors around implementation of CAB-LA. The project is in the initial implementation stage, with CAB-LA beginning to be rolled out at WVHR after the recent state Medicaid decision to drop prior authorization requirements for CAB-LA. The proposed study will utilize a digital health intervention with behavioral health economics and patient education from PRIME and Reciprocity to evaluate the adoption and implementation for PrEP adherence and persistence. The implementation aims of the study will leverage the RE-AIM framework as follows: Assessment of the digital health intervention will focus primarily on individual-level dimensions of RE-AIM, including reach and effectiveness. For example, in assessing reach of the digital health intervention, participant demographics will be compared to the intended audience to evaluate the extent to which populations with high unmet needs were engaged. Conversely, assessment of the implementation of CAB-LA will focus on system-level dimensions of RE-AIM, such as qualitative assessments of barriers to and facilitators for implementation of CAB-LA. Furthermore, evaluation of implementation outcomes will be based on the Proctor et al. conceptual framework, using specific measures developed by Weiner et al. to assess acceptability, appropriateness, and feasibility of the intervention. In addition, evaluation of PROs will be informed by a review of validated instruments, including HIVSTQ (HIV Treatment Satisfaction Questionnaire), SMSQ (Study Medication Satisfaction Questionnaire), I-TAQ (Injection Treatment Acceptance Questionnaire), ACCEPT (Chronic Treatment Acceptance Questionnaire), and the PrEP Stigma Scale, with survey items tailored to evaluate PrEP acceptance, satisfaction, and perceptions of PrEP-related stigma for both the CAB-LA and oral PrEP arms.

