6.14.1.4. Implementation Outcomes for the Mobile App

Acceptability of the mobile app to support patients in taking PrEP will be measured by the Acceptability of Intervention Measure (AIM) at months 1, 5, and 11. Appropriateness of the mobile app to support patients in taking PrEP will be measured by the Intervention Appropriateness Measure (IAM) at months 3, 9, and 12.

6.14.1.5. Clinic Staff Acceptability, Appropriateness, and Feasibility of Providing Long-acting Cabotegravir Injections

Acceptability of the process for providing long-acting cabotegravir injections will be assessed by the Acceptability of Intervention Measure (AIM). Appropriateness of the process for providing long-acting cabotegravir injections will be assessed by the Intervention Appropriateness Measure (IAM). Feasibility of long-term use of cabotegravir injections will be assessed by the Feasibility of Intervention Measure (FIM). Willingness to sustain provision of long-acting cabotegravir injections and barriers to and facilitators for provision of long-acting cabotegravir injections will be assessed through a brief survey. The clinic staff surveys will be administered at baseline, month 6, month 12, and end of study.

7. Statistical Analyses

Baseline analyses will include tabulations of demographic and clinical variables of the study participants. Chi-square tests and t-tests will be used to compare these groups to determine if baseline differences exist. The distribution of each continuous variable will be inspected for outliers to determine whether a parametric or non-parametric approach should be applied. The Wilcoxon ranked sum test will be used for any variable that does not meet the statistical assumptions of the t-test. Variables found to be associated with persistence or adherence following univariate analysis will be included in multivariate models.

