Appendix D: Clinician Instruments

PROVIDER SURVEY (Note: baseline survey)

Thank you for agreeing to be part of this quality improvement project to improve care for those individuals taking PrEP. Your responses will remain confidential and anonymous.

Part 1. Information About You and Your Patients

1. What year were you born? [Write in]
2. How do you describe your gender (response optional)? [Select 1]
 - Female
 - Male
 - Transgender woman
 - Transgender man
 - Non-binary
 - Prefer not to answer
 - A gender not listed: [Write in]
3. Which of the following best describes your racial/ethnic background (response optional)? (Select all that apply)
 - African American/Black
 - Asian/Pacific Islander
 - Caucasian/White

- Hispanic/Latinx
- Native American/Alaska Native
- A race or ethnicity not listed: [Write in]

4. What is your role within the interprofessional team? [Select 1]

- Physician
- Physician assistant
- Nurse practitioner
- Nurse
- Medical assistant
- Pharmacist
- Case manager
- Social worker
- Clinic administrative staff
- A role on the interprofessional team not listed: [Write in]

5. What is your role in the clinic for providing long-acting cabotegravir to your patients? (Select all that apply)

- Prescribing
- Medication procurement and/or dispensing
- Administering injections
- Patient scheduling
- Coordinating clinic flow (i.e., room availability, nurse scheduling, availability of injection during appointment, etc)
- Providing wraparound services (i.e., transportation, housing support, mental health resources, etc.)
- Patient counseling
- A role not listed: [write in]

Part 2. Acceptability, Appropriateness, and Feasibility of Implementing Long-Acting Cabotegravir Injections

Acceptability of Intervention Measure (AIM)

	Completely disagree	Disagree	Neither agree nor disagree	Agree	Completely agree
1. Our clinic process for providing long-acting cabotegravir injections to our clients meets my approval.					

2. Our clinic process for providing long-acting cabotegravir injections to our clients is appealing to me.					
3. I like our clinic process for providing long-acting cabotegravir injections to our clients.					

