Please indicate how much you agree with the following:

	Strongly agree	Agree	Neutral	Disagree	Strongly disagree
4. People experience negative judgment because they take PrEP.	()	()	()	()	()
5. Someone taking PrEP would be seen by others as slutty.	()	()	()	()	()

6. People taking PrEP receive praise for being responsible.	()	()	()	()	()
7. Someone taking PrEP would be treated unfairly by their doctors.	()	()	()	()	()

8. What barriers do you foresee in the implementation of long-acting cabotegravir for PrEP?

[Select up to 2]

- Patient's ability to keep bimonthly appointments
- Patient's transportation for bimonthly appointments
- Flagging/Clinic awareness of missed visits
- Staffing resourcing for clinic flow
- Rescheduling missed injections
- Patients acquiring HIV due to missed dose/visit
- Management of patients with other needs
- Patient injection/soreness

9. Which structural changes or resources may help facilitate long-acting cabotegravir implementation in your clinic? [Select up to 2]

- Increased coordination with other departments (i.e., pharmacy)
- Purchasing new refrigerators
- Finding room space or working around room availability
- Adjusting or extending staff working hours
- Use of different staff for injections
- Making transportation arrangements for patient participants
- Expanding hours for injection visits (i.e., visits in morning or during lunch breaks)
- Accommodating patients needing to reschedule injection visits (i.e. using walk-in visits, same-day appointments)
- Other: [write in]

10. How helpful do you think your clients will find the TheraPay mobile health app in supporting persistence with PrEP?

- Very helpful
- Somewhat helpful
- Neither helpful or unhelpful
- Somewhat unhelpful
- Very unhelpful

11. Do you have a preference for prescribing long-acting cabotegravir or daily oral PrEP?

- Prefer long-acting cabotegravir
- Prefer oral daily PrEP
- No preference

12. How likely is it that your clinic will continue to offer cabotegravir following the completion of this study?

- Very likely
- Somewhat likely
- Neutral
- Somewhat unlikely
- Very unlikely

Thank you for taking the time to complete this survey. Please provide your work email address. Your email will not be tied to your survey responses and will only be used for the purposes of this quality improvement initiative.

- Work email address: [Write in]

THANK YOU FOR COMPLETING THIS SURVEY.

PROVIDER SURVEY (Note: 6 months, 12 months and end of study)

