Thank you for agreeing to be part of this quality improvement project to improve care for those individuals taking PrEP. Your responses will remain confidential and anonymous.

Part 1. Information About You and Your Patients

6. What year were you born? [Write in]

7. How do you describe your gender? [Select 1]

- Female
- Male
- Transgender woman
- Transgender man
- Non-binary
- Prefer not to answer
- A gender not listed: [Write in]

8. Which of the following best describes your racial/ethnic background? (Select all that apply)

- African American/Black
- Asian/Pacific Islander
- Caucasian/White

- Hispanic/Latinx
- Native American/Alaska Native
- A race or ethnicity not listed: [Write in]

9. What is your role within the interprofessional team? [Select 1]

- Physician
- Physician assistant
- Nurse practitioner
- Nurse
- Medical assistant
- Pharmacist
- Case manager
- Social worker
- Clinic administrative staff
- A role on the interprofessional team not listed: [Write in]

10. What is your role in the clinic for providing long-acting cabotegravir to your patients? (Select all that apply)

- Prescribing
- Medication procurement and/or dispensing
- Administering injections
- Patient scheduling
- Coordinating clinic flow (i.e., room availability, nurse scheduling, availability of injection during appointment, etc)
- Providing wraparound services (i.e., transportation, housing support, mental health resources, etc.)
- Patient counseling
- A role not listed: [write in]

Part 2. Acceptability, Appropriateness, and Feasibility of Implementing Long-Acting Cabotegravir Injections

Acceptability of Intervention Measure (AIM)

	Completely disagree	Disagree	Neither agree nor disagree	Agree	Completely agree
1. Our clinic process for providing long-acting cabotegravir injections to our clients meets my approval.					

2. Our clinic process for providing long-acting cabotegravir injections to our clients is appealing to me.					
3. I like our clinic process for providing long-acting cabotegravir injections to our clients.					

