15. Please rate your confidence in **counseling** patients in HIV prevention, addressing barriers to using PrEP, and supporting persistence.
- Very high
 - High
 - Moderate
 - Low
 - Very low
 - Not applicable
16. Please rate the impact of providing long-acting cabotegravir injections for PrEP on your **workload** in clinic.
- Large increase in workload
 - Moderate increase in workload
 - No change in workload
 - Moderate decrease in workload
 - Large decrease in workload
17. What barriers have you observed with the implementation of long-acting cabotegravir for PrEP?
[Select up to 2]
- Patient's ability to keep bimonthly appointments
 - Patient's transportation for bimonthly appointments
 - Flagging/Clinic awareness of missed visits
 - Staffing resourcing for clinic flow
 - Rescheduling missed injections

- Patients acquiring HIV due to missed dose/visit
 - Management of patients with other needs
 - Patient injection/soreness
18. Which structural changes or resources have been most helpful in facilitating long-acting cabotegravir implementation in your clinic? [Select up to 2]
- Increased coordination with other departments (i.e., pharmacy)
 - Purchasing new refrigerators
 - Finding room space or working around room availability
 - Adjusting or extending staff working hours
 - Use of different staff for injections
 - Making transportation arrangements for patient participants
 - Expanding hours for injection visits (i.e., visits in morning or during lunch breaks)
 - Accommodating patients needing to reschedule injection visits (i.e. using walk-in visits, same-day appointments)
 - Other: [write in]
19. How could the process for use of long-acting cabotegravir injections for PrEP be improved? [Select up to 2]
- Increased clinic staff
 - Redistribution of clinic duties to allow dedicated healthcare providers more time to support long-acting cabotegravir processes
 - Regular evaluation of LA-CAB processes for efficacy and potential problems
 - Additional staff education/training
 - Improve documentation/EMR
 - Improve communication and care coordination within the clinical team
 - Improve communication with clients using PrEP (i.e. reminders of upcoming appointments, rescheduling of missed appointments)
 - Other: [fill in blank]
20. For participants who stopped taking long-acting injectable PrEP, which of the following best describes the most common reason(s) why? [Select up to 2]
- They no longer have an indication or need for PrEP

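### The clinician barrier item is a closed list with no 'Other', no 'None' and no coverage, cost or drug-supply option, so some answers to the barriers objective cannot be recorded

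*Combined protocol and SAP*

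**What the plan says.** Section 6.14.1.5 assigns barriers to and facilitators for CAB-LA provision to a brief survey and sets its timing: "The clinic staff surveys will be administered at baseline, month 6, month 12, and end of study". The clinician row of the Study Outcomes Table also assigns barriers to a brief survey, and it lists an interview next to the survey as data source, approach and instrument. Section 4.1 foresees "qualitative assessments of barriers to and facilitators for implementation of CAB-LA".

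In Appendix D, baseline item 8 asks "What barriers do you foresee in the implementation of long-acting cabotegravir for PrEP" and follow-up item 17 asks "What barriers have you observed with the implementation of long-acting cabotegravir for PrEP". Both offer the same eight fixed options, of which at most two may be chosen. The facilitator items (9 and 18) and the follow-up improvement item (19) end with a write-in.

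Both forms promise "Your responses will remain confidential and anonymous" and collect a work email with the assurance "Your email will not be tied to your survey responses". Neither carries a respondent code.

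Section 2.1 reports the state Medicaid decision to "remove all prior authorization requirements for CAB-LA for PrEP" and describes a site that serves uninsured and underinsured adults.

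**The concern.** Secondary objective 4 includes the barriers to implementing CAB-LA, and item 8/17 is the survey question that asks for them directly. A closed list returns only what its authors expected. If the main obstacle is not on the list, the results will show something else as the leading barrier, or nothing. If staff see no obstacle, the item cannot say so.

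Coverage is a plausible omission to matter. The background makes prior authorization the central access story, but describes its removal for Medicaid only. The patient baseline survey also provides for Medicare, private insurance and no insurance. Supply is another: the staff survey lists procurement and dispensing as a role, but people in that role have no supply option to tick. Answers not collected at a wave cannot be recovered afterwards.

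**Working it through.** No figure in the plan bears on this point. The sample size statement concerns patient adherence, Section 7 describes no analysis of the clinician data, and no staff number is given. The check is therefore a comparison of texts.

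**Step 1. Compare the barrier item with similar items.**

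| Item | Subject | Write-in | 'None' option | Coverage, cost or supply option |
|---|---|---|---|---|
| Staff, baseline 8 | barriers foreseen | no | no | no |
| Staff, follow-up 17 | barriers observed | no | no | no |
| Staff, baseline 9 and follow-up 18 | facilitators | yes | no | no (coordination with pharmacy is listed) |
| Staff, follow-up 19 | process improvement | yes | no | no |
| CAB-LA patient persistence assessment, question 4 | challenges | yes | yes | no |

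The patient form already uses both missing safeguards for the equivalent question.

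**Step 2. Classify the eight options of item 8/17.** Two concern keeping or travelling to appointments, two concern noticing and rescheduling missed visits, one concerns staffing, two concern consequences for the patient (HIV acquisition after a missed dose, and injection soreness), and one concerns patients with other needs. That is 2 + 2 + 1 + 2 + 1 = 8, and none concerns payer, price or stock.

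**Step 3. Follow a respondent who does not fit.** A respondent with no barrier to report must either tick something untrue or skip the item, and a skipped item looks the same as non-response. A respondent whose barrier is coverage or supply has the same two choices, or may force it into the option on other needs.

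**Step 4. Look for another route.** An interview could capture these answers. But Section 6.2.9 lists only the baseline and follow-up surveys with their scales, Appendix D contains only the two survey forms, and the clinic staff schedule in Appendix H shows no interview. The write-ins on items 9, 18 and 19 ask what helps or what could be improved, not what the barriers are.

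**Step 5. Check linkage of waves.** With anonymous answers, an unlinked email and no code, AIM, IAM and FIM can be summarised wave by wave but not in paired respondents. Both forms do ask "What year were you born? [Write in"], together with gender, race or ethnicity and role. Matching on these is not planned and would sit badly with the promise of anonymity.

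**The case against.** The best defence is that the survey is not the only listed source. The outcomes table names an interview and Section 4.1 a qualitative assessment, and either could record coverage, supply or the absence of barriers. That would answer the point if the interview were specified. It is not, and both the outcomes table and Section 6.14.1.5 assign barriers to the survey.

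A second defence is that coverage may matter little at this site: prior authorization has been dropped by Medicaid, and the in-house pharmacy gives uninsured patients access to free medicines. This is fair, and it weakens any claim that coverage is a leading barrier. It does not justify a form that cannot show whether it is.

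A reader might infer that the item misses the barriers the protocol itself names. The documents do not support that. The coverage barrier named is prior authorization, presented as removed, while appointments, transport and injection soreness are on the list.

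A reader might also infer that unlinked waves prevent secondary objective 4 from being met. That does not follow either. The objective is to evaluate and specifies no change within staff, and Section 4.1 directs this assessment at system-level dimensions. Four anonymous cross-sections give clinic-level estimates at each wave. They are less suited to describing change, because staff turnover is mixed in, but leaving answers unlinked is a legitimate choice in exchange for candour.

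Nor is the limit of two choices a defect: it is an ordinary way to ask for priorities, and a barrier is lost from pooled results only if nobody places it in their top two.

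**Conclusion.** The barrier item should be changed. As written it cannot record the absence of barriers or any barrier outside eight fixed options, at any of the four waves, and no other specified instrument asks staff about barriers directly. The effect is limited to one item of one secondary endpoint; no primary endpoint is touched. How many answers would be lost cannot be estimated, because the documents give neither the number of staff nor how common unlisted barriers are. The conclusion rests on the form as printed and on the interview remaining unspecified; a guide and schedule for it would narrow the gap.

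The absence of linkage is a trade-off to weigh, not a fault to correct.

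**What to change.** Add three options to items 8 and 17: 'Coverage, prior authorization, cost or drug supply', 'Other: [write in]' and 'None'. The cost is a slightly longer form.

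If the baseline survey has already been completed, the options will differ between baseline and follow-up, and the report should say so. Little comparability is lost, because the question already changes from barriers foreseen to barriers observed. The three later waves would still share one form if the change is made before month 6.

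Optionally, add a voluntary self-generated code so that AIM, IAM and FIM can also be summarised in paired respondents. Set this against the risk of re-identification at one clinic, where birth year, gender, race or ethnicity and role are already asked.

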including access to free medications for uninsured patients. Additionally, WVHR utilizes a mobile health clinic to care for hard-to-reach populations. WVHR is in Kanawha County, which is designated by the CDC as one of the top vulnerable areas of rapid spread of HIV due to injection drug use. Due to its location, services provided, and focus on uninsured/underinsured individuals, the populations cared for by WVHR encompass those with high unmet needs and PrEP-related disparities, including women, persons who inject drugs (PWID), transgender persons, persons in rural areas, and persons with low-income. Importantly, WVHR is committed to sustaining the HIV prevention initiative after the proposed study has concluded, as stated in the letter from Chief Executive Officer, [name], DNP, APRN, BC, FNP

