2. Secondary Endpoint: Retention-in-care	The proportion of patients presenting for their follow-up appointments within 30 days of their scheduled visit at months 3, 9 and 12 after PrEP initiation for the Oral PrEP arm and months 3, 9, and 11 for the CAB-LA arm.	Quantitative	M3, M9, M11, M12	Participant survey and EHR	Participant survey and EHR	Survey
3. Secondary Endpoint: PROs	PRO Set #1: PrEP Medication Satisfaction; PrEP-Related Stigma PRO Set #2: PrEP Acceptance ----- Barriers to adherence to CAB-LA injections and	Qualitative	M1, M5, M11 (PRO Set #1), M3, M9, M12 (PRO Set #2) Barriers to adherence in oral PrEP arm: M1, M2, M3, M4, M5,	Participant Survey	Patient questionnaire	Survey

	oral PrEP, and reasons for PrEP discontinuation will be assessed through brief behavioral surveys		M6, M7, M8, M9, M10, M11, M12 Barriers to adherence in CAB-LA PrEP arm: M1, M3, M5, M7, M9, M11			
4. Secondary Endpoint: Implementation Outcomes	Acceptability of Intervention Measure (AIM) and Intervention Appropriateness Measure (IAM) Health literacy evaluation and helpfulness of the education modules within the digital health program assessed through a brief survey	Qualitative	M3, M9, M12	Participant Survey	Patient questionnaire	Survey
5. Secondary Endpoint: Clinician Acceptability, Appropriateness, and Feasibility	Acceptability of Intervention Measure (AIM), Intervention Appropriateness Measure (IAM), and Feasibility of Intervention Measure (FIM)	Qualitative	M0, M6, M12, and End of Study	Clinician Survey, Interview	Clinician Survey, Interview	Clinician Survey, Interview

	Willingness to sustain provision of CAB-LA, barriers to and facilitators for provision of CAB-LA assessed through a brief survey					
--	--	--	--	--	--	--

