 - They found it too difficult to take PrEP as prescribed with their lifestyle
 - They felt stigmatized by others for taking PrEP
 - They experienced side effects from taking PrEP
 - They take too many medications
 - They felt there were too many appointments as part of PrEP care
 - They tested positive for HIV

21. How helpful do you think your clients find the TheraPay mobile health app in supporting persistence with PrEP?

- Very helpful
- Somewhat helpful
- Neither helpful or unhelpful
- Somewhat unhelpful
- Very unhelpful

22. Do you have a preference for prescribing long-acting cabotegravir or daily oral PrEP?

- Prefer long-acting cabotegravir
- Prefer oral daily PrEP
- No preference

23. How likely is it that your clinic will continue to offer cabotegravir following the completion of this study?

- Very likely
- Somewhat likely
- Neutral
- Somewhat unlikely
- Very unlikely

Thank you for taking the time to complete this survey. Please provide your work email address. Your email will not be tied to your survey responses and will only be used for the purposes of this quality improvement initiative.

- Work email address: [Write in]

THANK YOU FOR COMPLETING THIS SURVEY.

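### Staff willingness to keep providing CAB-LA is named as an outcome, but the only survey item on continuation asks for a forecast of what the clinic will do

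*Combined protocol and SAP*

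**What the plan says.** Section 6.14.1.5, on clinic-staff outcomes, lists "Willingness to sustain provision of long-acting cabotegravir injections and barriers to and facilitators for provision" of CAB-LA as matters for a brief survey given at baseline, month 6, month 12 and end of study. The Study Outcomes Table repeats this under the fifth endpoint, on clinicians: "Willingness to sustain provision of CAB-LA, barriers to and facilitators for provision of CAB-LA assessed through a brief survey". That row also lists an interview as a data source, but the documents contain no interview guide.

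The survey is in Appendix D. One item in it looks beyond the end of the study: "How likely is it that your clinic will continue to offer cabotegravir following the completion of this study". It is item 12 at baseline and item 23 at follow-up, with five answers from very likely to very unlikely.

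Section 2.1 (Background) states that "WVHR is committed to sustaining the HIV prevention initiative after the proposed study has concluded, as stated in the letter from Chief Executive Officer". That sentence concerns the prevention initiative as a whole and does not name CAB-LA.

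**The concern.** The outcome named is an attitude of staff. The item asks for a prediction about an institution. The two can separate in the case that the outcome should detect: a staff member who finds the injections burdensome and would rather stop, but who expects the clinic to carry on, can truthfully choose the most favourable answer.

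The role question (baseline item 4, follow-up item 9) shows that respondents may include nurses, medical assistants, case managers, social workers and administrative staff. The documents do not say who will decide whether CAB-LA stays on offer, but it is unlikely that all of these respondents will. For those who do not, the answer records what they expect of others.

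At stake is the label on a result. A high proportion answering likely could be published as staff willingness to sustain CAB-LA when it is partly, or mainly, staff expectation that the clinic will continue. A change in willingness over the four administrations could also be muted.

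**Working it through.** The plan states no figure for this outcome: no number of clinicians surveyed, no scoring rule and no threshold for a positive response. The one interval that it calculates, for the adherence difference between arms, does not bear on this point. The check is therefore mainly a comparison of wording.

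**Step 1. Compare the named outcome with the candidate items in Appendix D.**

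| Item | What it asks | Does it measure own willingness to continue? |
|---|---|---|
| Baseline 12, follow-up 23 | How likely the clinic is to keep offering cabotegravir | No: a forecast about the clinic |
| AIM, 4 items | Approval and liking of the clinic's current process | Indirect: 6.14.1.5 assigns it to acceptability |
| IAM, 4 items | Fit of the clinic's process | No: assigned to appropriateness |
| FIM, 4 items (item 4: ease of continuing) | Whether long-term use in the clinic is workable | Indirect: assigned to feasibility |
| Baseline 11, follow-up 22 | "Do you have a preference for prescribing long-acting cabotegravir or daily oral PrEP" | Indirect: product preference, and many listed roles do not prescribe |
| Follow-up 16 | Effect on the respondent's workload | Indirect: burden, and not asked at baseline |

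The remaining items cover demographics and roles, confidence, stigma, barriers, facilitators, process improvements, reasons patients stop, and usefulness of the app. None asks whether the respondent is willing to go on providing CAB-LA. The link from item 12/23 to the outcome is by elimination, because no text in the plan makes it.

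**Step 2. Check whether the survey could have asked personally.** It does so elsewhere. Confidence, workload and prescribing preference are all put to the respondent as their own. The clinic-level phrasing of item 12/23 is therefore not forced by the format.

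**Step 3. Illustrate how far a forecast can mask willingness.** All inputs here are assumptions. Let 95% of staff expect continuation. Let a share *a* answer the item as a forecast, and let the rest answer from their own willingness, *w*. Then

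proportion answering likely = 0.95*a* + (1 − *a*)*w*.

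| *a* | *w* = 30% | *w* = 90% | Visible spread |
|---|---|---|---|
| 0.50 | 0.475 + 0.150 = 62.5% | 0.475 + 0.450 = 92.5% | 30 points |
| 0.75 | 0.7125 + 0.075 = 78.75% | 0.7125 + 0.225 = 93.75% | 15 points |
| 1.00 | 95% | 95% | 0 points |

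The true spread is 60 points, and the item shows (1 − *a*) × 60 of it. The flat result in the last row follows directly from assuming that everyone answers purely as a forecast, so it is a limiting case and not an estimate.

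**The case against.** Five points can fairly be made for the plan.

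- **Unit of measurement.** The plan does not say that the willingness is personal. Section 4.1 says that the CAB-LA implementation assessment looks at system-level dimensions, and provision is something a clinic does. This has some force. But 6.14.1.5 and the outcomes table place the outcome under clinic staff and clinicians, and even a clinic's willingness differs from a staff member's estimate of whether the clinic will continue.
- **Mapping.** No text ties item 12/23 to this outcome. That is true, and it limits the point: a reader might infer that the outcome is not measured at all, which is more than the documents support. It also means that the plan leaves the measure unnamed.
- **Other signals.** A reluctant staff member could register on AIM, FIM item 4, workload or prescribing preference, or in an interview. This stands in part. These are real but indirect signals; the survey scales are assigned to other constructs, and no interview content is given.
- **The commitment.** A reader might infer from Section 2.1 that management has in effect announced the decision, so that item 12/23 will read near 100% whatever staff think. The documents do not support this. The letter covers the prevention initiative, which might continue without CAB-LA, and nothing says that staff know of it.
- **Sensitivity.** The five-point scale allows gradation, and answers may move as staffing or missed-injection problems emerge. In the 50% row of the illustration the item does discriminate.

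**Conclusion.** The mismatch holds on wording alone and needs no ceiling effect. The plan names staff willingness to continue providing CAB-LA, and the closest survey item records an expectation about the clinic. The commitment in Section 2.1 is a plausible source of upward pull on the answers, and no more than that. The claims that the item has no power to discriminate, or that falling willingness could never show, apply only if every respondent answers purely as a forecast, which the documents do not establish.

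The size cannot be computed from the documents. Under the assumed inputs, between half and all of the true variation in willingness would be hidden, depending on how respondents read the item. The conclusion rests on two readings: that the outcome concerns staff, as its placement indicates, and that item 12/23 is its intended measure, which is inferred. The consequence is small. This is one descriptive component of a secondary endpoint with no test or decision rule attached, and the comparison of persistence and adherence between arms is untouched. It is a worthwhile improvement because it is cheap.

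**What to change.** 1. Keep baseline item 12 and follow-up item 23 unchanged, and report them as expected continuation of CAB-LA at the clinic.
2. Add one item to both provider surveys on the respondent's own position, for example: *I am willing to continue my part in providing long-acting cabotegravir after this study.* Use the five-point agreement scale already used for AIM, IAM and FIM, with an added option *not applicable – no role*.
3. In 6.14.1.5 and row 5 of the Study Outcomes Table, name the new item as the measure of willingness to sustain provision.

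The cost is one extra item at each of the four administrations, under a minute per respondent, and a minor instrument amendment. If the baseline survey has already been given when the change is made, the new item will have no baseline value and should be reported from the first administration that carries it.
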